### 6.2.2. Efficacy Procedures

A variety of parameters will be collected during the study to assess efficacy/effectiveness of dupilumab, including measures of AD severity, use of concomitant treatment for AD, and patient-reported measures of AD symptoms and QOL.

Questionnaires and patient-reported assessments should be administered prior to obtaining investigator assessments, safety and laboratory assessments, and study drug administration. Please see study manual for instructions on the administration and use of all patient-reported instruments (including Pruritus NRS, patient global assessment of disease, patient global assessment of treatment, Children's Dermatology Life Quality Index [CDLQI], Patient Oriented Eczema Measure [POEM], and Hospital Anxiety and Depression Scale [HADS]).

#### 6.2.2.1. Patient Assessment of Pruritus Using Numerical Rating Scale

The Pruritus NRS is a simple assessment tool that patients will use to report the intensity of their pruritus (itch) during a 24-hour recall period. Patients will be asked the following question:

For maximum itch intensity: "On a scale of 0 to 10, with 0 being 'no itch' and 10 being the 'worst itch imaginable', how would you rate your itch at the worst moment during the previous 24 hours?"

Patients will be instructed on using the patient diary to record their Pruritus NRS score at the screening and baseline visits. Patients will complete the rating scale DAILY throughout the entire study (screening period, treatment period, and follow-up period; see time point in section 6.1). Clinical sites will check and remind patient to complete the diary at each visit.

### 6.2.2.2. Patient Assessment of Pruritus Using Pruritus Categorical Scale

The pruritus categorical scale is a 4-point scale used to assess symptoms that has been used in previous clinical studies of AD, and there is less of a tendency for patients to provide an “average” response than there might be with a 5-point scale (Kaufmann 2006). The scale is rated as follows: 0 = absence of pruritus; 1 = mild pruritus (occasional slight itching/scratching); 2 = moderate pruritus (constant or intermittent itching/scratching that does not disturb sleep); and 3 = severe pruritus (bothersome itching/scratching that disturbs sleep). Patients will be instructed on using the patient diary to record their pruritus categorical scale score at the screening and baseline visits. Patients will complete the rating scale DAILY throughout the entire study (screening period, treatment period, and follow-up period; see time point in section 6.1). Clinical sites will check and remind patient to complete the diary at each visit.

### 6.2.2.3. Patient Global Assessment of Disease

Patients will rate their disease based on the 5-level scale as follows:

Overall, how would you rate your eczema symptoms right now?

- No symptoms
- Mild symptoms
- Moderate symptoms
- Severe symptoms
- Very severe symptoms

Patients will undergo this assessment at time points according to section 6.1.

The assessment tool is provided in the study reference manual.

### 6.2.2.4. Patient Global Assessment of Treatment

Patients will respond to the following question based on the 5-level scale as follows:

Compared to before you started the study, how would you rate your eczema symptoms now?

- Much better
- A little better
- No difference
- A little worse
- Much worse

Patients will undergo this assessment at time points according to section 6.1.

The assessment tool is provided in the study reference manual.

#### 6.2.2.5. Children's Dermatology Life Quality Index

The CDLQI is a validated questionnaire designed to measure the impact of skin disease on the QOL in children (Lewis-Jones 1995). The aim of the questionnaire is to measure how much a patient's skin problem has affected the patient over a recall period of the past week. To complete the questionnaire, patients need to provide responses to 10 questions (the questions focus on domains such as symptoms feelings associated with disease, the impact of the disease on leisure, school or holidays, personal relationships, sleep, and side effects of treatment for the skin disease. The instrument has a recall period of 7 days. Nine of the 10 questions are scored as follows:

- Very much = 3
- Quite a lot = 2
- Only a little = 1
- Not at all = 0
- Question unanswered = 0

Question 7 has an additional possible response (prevented school), which is assigned a score of 3.

The CDLQI for a patient is the sum of the score of each question with a maximum of 30 and a minimum of 0. The higher the score, the greater the impact is on the QOL. The CDLQI can also be expressed as a percentage of the maximum possible score of 30.

Patients will undergo this assessment at time points according to section 6.1.

The CDLQI is provided in the study reference manual.

#### 6.2.2.6. Patient Oriented Eczema Measure

The POEM is a 7-item, validated questionnaire used in clinical practice and clinical trials to assess disease symptoms in children and adults (Charman 2004). The format is a response to 7 items (dryness, itching, flaking, cracking, sleep loss, bleeding, and weeping) based on frequency of these disease symptoms during the past week (ie, 0 = no days, 1 = 1 to 2 days, 2 = 3 to 4 days, 3 = 5 to 6 days, and 4 = all days) with a scoring system of 0 to 28; the total score reflects disease-related morbidity. The questionnaire will be administered at time points according to section 6.1.

#### 6.2.2.7. Patient-Assessed Hospital Anxiety and Depression Scale

The HADS is an instrument for screening anxiety and depression in non-psychiatric populations; repeated administration also provides information about changes to a patient's emotional state (Zigmond 1983, Herrmann 1997). The HADS consists of 14 items, 7 each for anxiety and depression symptoms; possible scores range from 0 to 21 for each subscale. The following cut-off scores are recommended for both subscales: 7 to 8 for possible presence, 10 to 11 for probable presence, and 14 to 15 for severe anxiety or depression. The questionnaire will be administered only to the subset of patients who fluently speak a language in which the

questionnaire is presented (based on availability of validated translations in participating countries), at time points according to section 6.1.

The HADS is provided in the study reference manual.

#### **6.2.2.8. Juniper Asthma Control Questionnaire – 5**

The 5-question version of the Juniper Asthma Control Questionnaire (ACQ) is a validated questionnaire to evaluate asthma control. The questionnaire will be administered only to the subset of patients with ongoing asthma and who fluently speak a language in which the questionnaire is presented (based on availability of validated translations in participating countries), at time points according to section 6.1.

The assessment tool is provided in the study reference manual.

#### **6.2.2.9. Total Nasal Symptom Score**

The Total Nasal Symptom Score (TNSS) will be used to assess the effect of study drug on symptoms of allergic rhinitis. The summed score will include the following 5 symptoms: rhinorrhea, nasal congestion, nasal itching, sneezing, and difficulty in sleeping, each rated on a 0 to 3 scale of severity. This instrument has been extensively used in previous trials conducted in patients with allergic rhinitis (Berger 2015, Benninger 2010). The questionnaire will be administered only to the subset of patients with a medical history of allergic rhinitis who fluently speak a language in which the questionnaire is presented (based on availability of translations in participating countries). Patients will be instructed on using the patient diary to record their TNSS throughout the screening period (at least 7 days before baseline/day 1) and only for 7 days preceding visit 6, visit 18, and visit 21.

The assessment tool is provided in the study reference manual.

#### **6.2.2.10. Injection Site Pain Visual Analogue Scale**

Patients will be asked to provide an assessment of pain experienced during injection of study drug using a Visual Analogue Scale (VAS). This assessment will be performed after injection of the study drug at certain in-clinic visits according to section 6.1.

The assessment tool is provided in the study reference manual.

#### **6.2.2.11. Investigator's Global Assessment**

The IGA is an assessment instrument used in clinical studies to rate the severity of AD globally, based on a 5-point scale ranging from 0 (clear) to 4 (severe). The IGA score will be assessed at time points according to section 6.1.

The IGA is provided in the study reference manual and in Appendix 2.

#### 6.2.2.12. Eczema Area and Severity Index

The EASI is a validated measure used in clinical practice and clinical trials to assess the severity and extent of AD (Hanifin 2001). The EASI is a composite index with scores ranging from 0 to 72. Four AD disease characteristics (erythema, thickness [induration, papulation, edema], scratching [excoriation], and lichenification) will each be assessed for severity by the investigator or designee on a scale of “0” (absent) through “3” (severe). In addition, the area of AD involvement will be assessed as a percentage by body area of head, trunk, upper limbs, and lower limbs, and converted to a score of 0 to 6. In each body region, the area is expressed as 0, 1 (1% to 9%), 2 (10% to 29%), 3 (30% to 49%), 4 (50% to 69%), 5 (70% to 89%), or 6 (90% to 100%). The EASI will be collected at time points according to section 6.1.

The EASI assessment tool is provided in the study reference manual.

#### 6.2.2.13. Global Individual Signs Score

Individual components of the AD lesions (erythema, infiltration/papulation, excoriations, and lichenification) will be rated globally (ie, each assessed for the whole body, not by anatomical region) on a 4-point scale (from 0=none to 3=severe) using the EASI severity grading criteria (section 6.2.2.12). The Global Individual Signs Score (GISS) will be assessed at time points according to section 6.1.

The GISS assessment tool is provided in the study reference manual.

#### 6.2.2.14. SCORing Atopic Dermatitis

The SCORing Atopic Dermatitis (SCORAD) is a validated tool used in clinical research and clinical practice that was developed to standardize the evaluation of the extent and severity of AD (European Task Force on Atopic Dermatitis 1993). There are 3 components to the assessment: A = extent or affected BSA, B = severity, and C = subjective symptoms. The extent of AD is assessed as a percentage of each defined body area (see section 6.2.2.15) and reported as the sum of all areas, with a maximum score of 100% (assigned as “A” in the overall SCORAD calculation). The severity of 6 specific symptoms of AD (redness, swelling, oozing/crusting, excoriation, skin thickening/lichenification, and dryness) is assessed using the following scale: none (0), mild (1), moderate (2), or severe (3) (for a maximum of 18 total points, assigned as “B” in the overall SCORAD calculation). Subjective assessment of itch and sleeplessness is recorded for each symptom by the patient or relative on a Visual Analogue Scale, where 0 is no itch (or sleeplessness) and 10 is the worst imaginable itch (or sleeplessness), with a maximum possible score of 20. This parameter is assigned as “C” in the overall SCORAD calculation. The SCORAD is calculated as:  $A/5 + 7B/2 + C$  where the maximum is 103. Patients will undergo this assessment at time points according to section 6.1.

The SCORAD assessment tool is provided in the study reference manual.

**6.2.2.15. Body Surface Area Involvement of Atopic Dermatitis**

Body surface area affected by AD will be assessed for each section of the body using the rule of nines (the possible highest score for each region is: head and neck [9%], anterior trunk [18%], back [18%], upper limbs [18%], lower limbs [36%], and genitals [1%]) and will be reported as a percentage of all major body sections combined. Patients will undergo this assessment at time points according to section 6.1.

The BSA assessment tool is provided in the study reference manual.

**6.2.2.16. Assessment of Missed School Days**

Patients who are enrolled in school will be asked to report the number of missed school days since the last study assessment. Patients will undergo this assessment at time points according to section 6.1.

The assessment tool is provided in the study reference manual.

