Patient-reported TNSS h,i,k		X				X								
Patient assessment of injection pain using VAS h		X		X		X				X				X
IGA, EASI, GISS, SCORAD, BSA	X	X	X	X	X	X				X				X
Assess missed school days		X				X				X				X
Photograph AD areas (select sites)		X												
Safety:d														
Weight	X	X												
Height	X													
Vital signs	X	X l	X	X l	X	X l				X				X
Physical examination	X													
ECG	X													
Adverse events	X	X l	X	X l	X	X l	X	X	X	X	X	X	X	X

	Screening	Treatment Period												
		BL												
In-clinic Visit (V) or Phone Visit (PV)	V1	V2	V3	V4	V5	V6	PV7 a	PV8 a	PV9 a	V10	PV11 a	PV12 a	PV13 a	V14
Week (W)			W1	W2	W3	W4	W5	W6	W7	W8	W9	W10	W11	W12
Study Day (D)	D-35 to D-1	D1	D8	D15	D22	D29	D36	D43	D50	D57	D64	D71	D78	D85
Window in days			±3	±3	±3	±3	±3	±3	±3	±3	±3	±3	±3	±3
Laboratory Testing: d														
Hematology	X	X				X				X				
Chemistry m	X	X				X				X				
Urinalysis m	X	X				X								
Alcohol & drug screen test	X													
Pregnancy test, WOCBP only	Serum	Ur	Ur	Ur	Ur	Ur				Ur				Ur
HIV, HBsAg, HBsAb, HBcAb, Hep C Ab, TB l	X													
Biomarker: d														
TARC	X	X		X		X				X				X
Total serum IgE, immunoglobulin profiling, antigen specific IgE	X	X				X				X				X
Biomarker samples (serum)		X				X				X				
[REDACTED]														
[REDACTED]		X												
Drug Concentration and ADA: d														
Functional dupilumab concentration sample		X		X		X				X				X
ADA sample		X				X								

BL = baseline; Ur = urine; WOCBP = women of childbearing potential; TB = tuberculosis

a The site will contact the patient/caregiver by telephone to conduct these visits. The patient/caregiver may administer study drug during phone visits. Patients who receive study drug outside the study center will complete a dosing diary to document compliance with study drug administration and to document any related issues.

[REDACTED]

- c Training of patients regarding completion of diary to record (1) completion of assessment of Pruritus NRS scale, (2) completion of assessment of Pruritus Categorical Scale, (3) completion of assessment of Total Nasal Symptoms Score (TNSS), and (4) emollient usage.

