Drug Concentration and ADA Samples:c									
Functional dupilumab concentration sample				X			X	X	X
ADA sample				X			X	X	X

EOT = End of Treatment; EOS = End of Study

a The site will contact the patient/caregiver by telephone to conduct these visits. The patient/caregiver may administer study drug during phone visits. Patients who receive study drug outside the study center will complete a dosing diary to document compliance with study drug administration and to document any related issues.

b Unscheduled visits may be necessary to repeat testing following abnormal laboratory results, for follow-up of AEs, or for any other reason (eg, before a rescue medication/procedure is used), as warranted.

c Assessments/procedures should be conducted in the following order: patient reported outcomes (other than patient assessment of injection pain), investigator assessments, and safety and laboratory assessments (including sample collection for ADA, PK, and biomarkers). Samples positive in the ADA assay will be analyzed in the neutralizing antibody (NAb) assay.

d Patients or parents/caregivers will return the study kit box (for prefilled syringes) at each subsequent in-clinic visit. At these in-clinic visits, sites will perform accountability assessment for the study drug that the patients or parents/caregivers have returned to the site.

e Patient-reported assessments are to be completed only by the patient.

f The questionnaires will be administered only to the subset of patients who speak fluently the language in which the questionnaire is presented (based on availability of validated translations in participating countries).

g ACQ-5 will be administered only to patients with ongoing asthma.

h Total Nasal Symptoms Score will be administered only to patients with medical history of allergic rhinitis for 7 days preceding visit 18 and visit 21.

i The follow-up period will be for those patients who decline to enter the open-label extension study.

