#### 4.4.3. Other Efficacy Variables

Other efficacy endpoints include:

- Proportion of patients with SCORAD-50 ( $\geq 50\%$  reduction in SCORAD from baseline) response at week 16
- Proportion of patients with SCORAD-75 ( $\geq 75\%$  reduction in SCORAD from baseline) response at week 16
- Proportion of patients with SCORAD-90 ( $\geq 90\%$  reduction in SCORAD from baseline) response at week 16
- Patient global assessment of disease: proportion of patients with no symptom and proportion of patients with no symptom or mild symptoms at week 16
- Patient global assessment of treatment: proportion of patients who rate their eczema symptoms as “much better” at week 16
- Pruritus categorical scale: proportion of patients who achieve absence of pruritus or mild pruritus at week 16
- Proportion of patients who achieve reduction of IGA score by  $\geq 2$  from baseline to week 16
- Change in ACQ-5 score from baseline at week 16
- Change in weekly averaged TNSS score from baseline at week 16
- Change from baseline to week 16 in GISS (erythema, infiltration/papulation, excoriations, lichenification)
- Number of missed school days assessment during the treatment period
- Mean score of injection site pain as assessed by visual analogue scale for all visits through week 16

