### 5.7.4. Analyses of Other Efficacy Variables

The analyses of other efficacy variables will be the same as the primary analysis described in Section 5.7.1 and Section 5.7.2.

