#### 6.4. Analysis Visit Window

Data analyzed by-visit-analysis (including efficacy, laboratory data, visit sign, and ECG) will be summarized by the study scheduled visits described in the study protocol and SAP, “Schedule of Event”. The analysis visit windows will be exhaustive so that all available values obtained from unscheduled visits, early termination (ET) visit and end of treatment (EOT)/end of study (EOS) have the potential to be summarized. No analysis visit windows will be applied for the study scheduled visits.

The following analysis visit windows will be used to map the unscheduled visits, ET and EOT/EOS visits, based on the study day:

Visit	Target Day	Analysis Time Window Based on Study day*
Screening	<1	<1
Baseline	1	1
Week 1	8	[2,11]
Week 2	15	[12,18]
Week 3	22	[19,25]
Week 4	29	[26, 43]
Week 8	57	[44, 71]
Week 12	85	[72, 99]
Week 16	113	[100, 127]
Week 20	141	[128, 155]
Week 24	169	[156, 183]
Week 28	197	>=184

\*study day is calculated relative to the date of first study drug injection.

In general, the following order will be used to select the record for analysis at given visit:

1. Scheduled visit
2. Early termination (ET) or end of study (EOS), whichever comes first if scheduled visit not available
3. Unscheduled visit if both scheduled visit and ET/EOT/EOS are not available

For the multiple measurements of the same test in the same window, the following rules will be used to pick up the analysis value:

- If multiple valid values of a variable within an analysis visit window, the closest from the target study day will be selected.
- If the difference is a tie, the value after the targeted study day will be used.

- If multiple available values of a variable exist within a same day, then the first value of the day will be selected.

Both scheduled and unscheduled measurements will be considered for determining abnormal/PCSV values from laboratory, vital sign or ECG as well as the baseline values.

For the daily collected ePRO except TNSS data, the analysis visit windows will be implemented following the procedure below:

Step 1: Derive the study day

- If diary date  $\geq$  1st injection date, then diary study day = diary date – 1st injection date +1
- Otherwise diary study day = diary date – 1st injection date

Step 2:

- Windows are defined as -6 to 1 = BL, 2 to 8 = week 1, 9 to 15 = week 2, etc., with 7 days interval between visit windows.

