Parameter(s)	Endpoints	Primary Statistical Method	Supportive/Sensitivity Statistical Method	Subgroup Analysis
Global Individual Signs Score (GISS)	
 
• % change from baseline
 
• Change from baseline
 
	
 
• Multiple imputation (MI) with ANCOVA for continuous variables
 
	No	No
Patient Oriented Eczema Measure (POEM)	
 
• % change from baseline
 
• Change from baseline
 
	
 
• Multiple imputation (MI) with ANCOVA for continuous variables
 
	No	No
Children Dermatology Life Quality Index (CDLQI)	
 
• Change from baseline
 
	
 
• Multiple imputation (MI) with ANCOVA for continuous variables
 
	No	No
Hospital Anxiety and Depression Scale (HADS)	
 
• % change from baseline
 
• Change from baseline
 
	
 
• Multiple imputation (MI) with ANCOVA for continuous variables
 
	No	No
Patient Global Assessment of Disease Status	
 
• Number (%) of patients with no symptom
 
• Number (%) of patients with no symptom or mild symptoms
 
	
 
• CMH test adjusted by randomization strata
 
	No	No
Patient Global Assessment of Treatment	
 
• Number (%) of patients who rate their eczema symptoms as “much better”
 
	
 
• CMH test adjusted randomization strata
 
	No	No
Assess sick-leave/missed school days	
 
• Number (%) of patients
 
	
 
• Descriptive statistics by visit/time
 
	No	No
TNSS	
 
• Change from baseline
 
	
 
• Multiple imputation (MI) with ANCOVA for continuous variables
 
	No	No
VAS score of injection site pain	
 
• Mean value
 
	
 
• Descriptive statistics
 
	No	No

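### Missed school days are an interval count, but the by-visit summary keeps one record per visit, so most answers given at unscheduled visits are passed over

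*Protocol*

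**What the plan says.** Protocol 6.2.2.16 defines the item: "Patients who are enrolled in school will be asked to report the number of missed school days since the last study assessment". No fixed recall length is given.

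The schedules of events (Protocol Tables 1 and 2, repeated in SAP 10.2) carry a row "Assess missed school days". It is marked at day 1, at weeks 4, 8, 12, 16, 20, 24 and 28, and at unscheduled and early termination (ET) visits. It is not marked at screening, at weeks 1 to 3 or at the phone visits. A footnote to Protocol Table 2 says when unscheduled visits arise: "Unscheduled visits may be necessary to repeat testing following abnormal laboratory results, for follow-up of AEs, or for any other reason". It gives a visit before rescue as an example.

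The SAP treats the item in four places:

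- SAP 4.4.3 lists the endpoint as "Number of missed school days assessment during the treatment period".
- SAP Appendix 10.1 gives the endpoint as counts and percentages of patients and the method as "Descriptive statistics by visit/time". No sensitivity or subgroup analysis is planned.
- SAP 5.7.4 says of this group of variables: "The analyses of other efficacy variables will be the same as the primary analysis described in Section 5.7.1 and Section 5.7.2".
- SAP 6.4 governs by-visit data, efficacy included. It maps unscheduled visits to windows by study day and ranks records: scheduled first, then ET or end of study. Third comes "Unscheduled visit if both scheduled visit and ET/EOT/EOS are not available". Where several values share a window, "If multiple valid values of a variable within an analysis visit window, the closest from the target study day will be selected".

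**The concern.** Choosing one record per window suits a status measure such as IGA or EASI, where each value describes the patient on that day and an extra value is redundant. An interval count is different. Each answer holds days that no other answer holds, and asking the question again restarts the recall. If the answer from an unscheduled visit is then set aside, the days reported there are not picked up by the next scheduled answer.

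The result would be by-visit figures that cover unequal lengths of time and understate absence for patients with unscheduled visits. The only method stated specifically for this item would then fall short of the treatment-period number that SAP 4.4.3 names.

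**Working it through.** The documents state no rate, sample size or precision for this item, so there is no figure to reproduce. The check applies the SAP 6.4 rules to one unscheduled visit placed on each possible day.

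**Inputs**
- Question asked on days 1, 29, 57, 85 and 113 (Protocol Tables 1 and 2): four intervals of 28 days, 4 × 28 = 112 days.
- Windows (SAP 6.4): week 1 = 2–11, week 2 = 12–18, week 3 = 19–25, week 4 = 26–43, week 8 = 44–71, week 12 = 72–99, week 16 = 100–127.
- Assumptions: scheduled visits are attended on their target days, there is one unscheduled visit, and the recall runs from the last time this question was asked.

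**Formulas.** For an unscheduled visit on day *u*, between school-days assessments on days *a* and *b*:
- recall held in the unscheduled record = *u* − *a*
- recall held in the next scheduled record = *b* − *u*
- if the window containing *u* already holds a scheduled school-days record, the unscheduled record is passed over and *u* − *a* days of recall are lost.

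| Unscheduled day | Window | Scheduled school-days record in that window? | Recall in unscheduled record | Recall in next scheduled record |
|---|---|---|---|---|
| 15 | week 2 | no | 14 | 14 |
| 28 | week 4 | yes | 27 (lost) | 1 |
| 30 | week 4 | yes | 1 (lost) | 27 |
| 45 | week 8 | yes | 16 (lost) | 12 |
| 50 | week 8 | yes | 21 (lost) | 7 |
| 112 | week 16 | yes | 27 (lost) | 1 |

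**All possible days**
- Days 2 to 112 without the scheduled days 29, 57 and 85: 111 − 3 = 108 days.
- Days 2 to 25 (24 days) map to weeks 1 to 3, where the item is not scheduled, so the record is not displaced.
- The other 84 days (26 to 28, and 81 days after day 29) map to a window that already holds a scheduled record.
- Loss on days 26 to 28: 25 + 26 + 27 = 78 days.
- Loss after day 29: three intervals, each with losses of 1 to 27 days, mean 14.0, so 81 × 14 = 1,134 days.
- Mean loss per passed-over record: (78 + 1,134) / 84 = 14.4 days, or 14.4 / 112 = 12.9% of the treatment period. After day 29 alone: 14.0 / 112 = 12.5%.
- Range: 1 to 27 days; the maximum is 27 / 112 = 24.1%.
- Averaged over all 108 days, counting days 2 to 25 as no loss: 1,212 / 108 = 11.2 days, or 10.0%.

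**Illustration with invented answers.** Suppose an unscheduled visit on day 45 records 5 missed days and the week-8 visit on day 57 records 1. The week-8 row shows 1, from 12 days of recall. The 5 days, from 16 days of recall, are not in the by-visit summary. A sum would give 6 days over 28.

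**After the fix.** Summing gives (*u* − *a*) + (*b* − *u*) = 28 in every interval, so all 112 days are covered wherever the unscheduled visit falls.

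**The case against.** The strongest reply is that SAP 6.4 governs by-visit data, whereas SAP 4.4.3 names a quantity for the whole period. Adding up the raw records would fit 4.4.3 and lose nothing. That stands in part. Such a sum is not excluded, so a reader who infers that the unscheduled answers appear nowhere in the analysis goes further than the documents. But no sum is specified. The method given for the item is by visit, and the methods that SAP 5.7.4 points to contain no rule for adding records either.

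Other stronger readings also fail:

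- *Every unscheduled record is lost.* Records from days 2 to 25 can appear under weeks 1 to 3, although the week-4 answer is still shortened. An unscheduled record is also used when the scheduled and ET/EOT/EOS records are absent.
- *The missing time denominator causes the loss.* It does not. Record selection does, and a denominator alone would not bring the days back. A denominator is needed only for comparability.
- *The loss falls more on placebo and shrinks the treatment difference.* The documents do not give the frequency of unscheduled visits in either arm. The table footnote names laboratory repeats and AE follow-up as well as rescue, and Protocol 5.3 makes the pre-rescue visit optional.
- *Each answer covers only the week since the last phone contact.* The question is not asked at phone visits, so the natural reading is the last time it was asked. The assessment tool is in the study reference manual, which is not among the documents and may settle the wording.
- *A missed visit distorts the total.* The next answer then spans 8 weeks and recovers the time. Only the by-visit rows are affected.

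**Conclusion.** The point holds for the by-visit summary. If scheduled visits take place on their target days, an unscheduled visit on any day from 26 to 112 costs 1 to 27 days of recall, on average about 14 of 112. These are shares of one patient's recall time for one unscheduled visit, not shares of missed school days and not an effect on an arm. The effect on the difference between arms is unknown in size and direction. Separately, the treatment-period number in SAP 4.4.3 has no derivation, and SAP 5.7.4 and Appendix 10.1 point to different methods.

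The consequence is small. The item is among the other efficacy variables, is listed as descriptive, and is absent from the protocol's primary and secondary endpoints and from the testing hierarchy. The primary result and type I error are untouched. It is worth correcting because the data are already collected and the better derivation costs almost nothing.

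**What to change.** In SAP 4.4.3 and Appendix 10.1, define the endpoint as the sum of missed school days over all records after day 1 (scheduled, unscheduled and ET) up to the week-16 visit. Report it with the time those records cover, for example per 4 weeks observed. Leave the day-1 answer out of the sum: it precedes treatment, and no earlier school-days question anchors it. State in SAP 6.4 that this item is exempt from one-record selection, and in SAP 5.7.4 that its analysis is descriptive.

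Optionally, reword Protocol 6.2.2.16 so that the recall runs *since this question was last asked*.

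The cost is a few lines of SAP text and a little programming, with no new data. One limit remains: calendar weeks do not adjust for school holidays, so the result is a rate per observed time and not per school day.
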